5.2 Subject Exclusion Criteria

1. Presence of orthodontic appliances or removable partial dentures;
2. Presence of a soft tissue tumor of the oral cavity;
3. Presence of gross plaque or calculus as determined by the investigator;
4. Presence of extensive restorations that could affect the marginal gingiva (at the investigator's discretion);
5. Preexisting oral pathology requiring immediate treatment or ulcerations of the mucosa;
6. Preexisting carious lesions requiring immediate treatment (if a subject meets this criterion, he/she may be rescreened for study participation when he/she no longer meets this exclusion criterion);
7. Current participation in another clinical trial or product test;
8. Pregnant or breastfeeding;
9. Residence in the same household as a subject currently enrolled in the study (due to potential blinding and compliance issues);

10. Periodontal therapy other than prophylaxis within the past 6 months or endodontic therapy within 1 month of enrollment (if a subject meets this criterion, he/she may be rescreened for study participation when he/she no longer meets this exclusion criterion);
11. History of early onset periodontitis or acute necrotizing ulcerative gingivitis;
12. Chronic disease with concomitant oral manifestations, such as autoimmune or immunosuppressive diseases (e.g., human immunodeficiency virus, severe combined immunodeficiency, neutropenia, juvenile arthritis, systemic lupus erythematosus, sickle cell anemia, Crohn's disease, rheumatoid arthritis, Sjögren's syndrome) or immunocompromised status due to cancer chemotherapy, hematopoietic stem cell or solid organ transplant, head and neck radiotherapy, splenectomy, chronic corticosteroid usage;
13. Recent history of chronic alcohol consumption of more than five 1.5-ounce servings of 80-proof distilled spirits, five 12-ounce servings of beer, or five 5-ounce servings of wine per day;
14. Tobacco use (former tobacco users may be enrolled, provided they have been tobacco-free for 1 year or more);
15. Diabetes mellitus;
16. Subjects with urinalysis results suggestive of infection (if a subject meets this criterion, he/she may be rescreened for study participation when he/she no longer meets this exclusion criterion);
17. Medical conditions that the investigator considers significant and that may interfere with the examination or the safety of the subject;
18. Chronic (2 weeks or more) use of medication known to affect periodontal status within 1 month of enrollment, such as ≥ 81 mg aspirin per day, phenytoin, calcium antagonists such as nifedipine, NSAIDs, warfarin, cyclosporine, ≥ 10 mg/day atorvastatin or equivalent dose of another statin ([Subramanian, Emami et al. 2013](#)) (if a subject meets this criterion, he/she may be rescreened for study participation when he/she no longer meets this exclusion criterion);
19. Treatment with antibiotics within 1 month prior to enrollment (if a subject meets this criterion, he/she may be rescreened for study participation when he/she no longer meets this exclusion criterion);

20. Medical condition for which antibiotic treatment during the study period is likely or a condition for which antibiotic prophylaxis is recommended before dental procedures (American Heart Association 2007 guidelines [Geist, Fitzpatrick et al. 2007] will be followed);
21. Known hypersensitivity to any component of the test or placebo products;
22. Anything that, in the opinion of the investigator, would place the subject at increased risk or prevent the subject from fully complying with or completing the study.

The on-site medical monitor will review all laboratory test results and ensure that subjects meet the inclusion criteria for the study and do not meet any exclusion criteria. Additionally, the on-site medical monitor will decide whether subjects with an abnormal laboratory test result should have the laboratory test repeated. Subjects with a second abnormal laboratory test result will be referred to their primary care physician.

5.3 Strategies for Recruitment and Retention

Enrollment of 125 subjects is expected to take place over approximately 30 months. Having an already identified subject pool at the Forsyth Institute Center for Clinical and Translational Research (CCTR) should allow recruitment of subjects required to conduct the study in a timely manner. Subjects will be recruited from the CCTR subject pool, from area health centers, and through advertisements in local newspapers and electronic media outlets. All recruitment information and advertising will be submitted to the Institutional Review Board (IRB) prior to release.

Prospective subjects will receive a free periodontal examination and close dental and periodontal surveillance during the study. In addition, each subject will be compensated for visits attended, and parking fees will be paid for individuals who attend screening or study visits.

Subjects who miss a scheduled visit without notifying the study staff will be contacted by telephone, email, or text message to encourage their continued participation in the study and provide them with another appointment. If the subject declines further participation, he/she will be referred to a qualified practitioner for continued care. If a subject cannot be contacted by one of the methods listed above or he/she does not keep the next scheduled appointment, he/she will be sent a certified letter advising of the need for further follow-up and offering referral to a qualified practitioner for continued care.

Every effort will be made to encourage full participation until the end of the study. If a participant appears to be considering ending participation in the study, specific retention activities will be conducted to encourage him or her to continue. Strategies to promote adherence to study requirements will include after-hours visits for those who have tight work or personal schedules. To encourage compliance with study procedures, participants will be provided written instructions for product use and important details about the study protocol, and will be reminded of these at each study visit and with phone calls. Based on the participant's preferred communication method, reminder postcards, emails, telephone calls, and/or telephone texts will be provided prior to clinic visits. Appointment cards with important information on the reverse side (for example, contact person and phone number in case of an AE) will be given to all subjects after each completed visit.

5.4 Treatment Assignment Procedures

5.4.1 Randomization Procedures

Subjects will be assigned to treatment groups using a block randomization schedule.

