Following the Screening Visit, individuals with gingivitis or periodontitis who are not eligible for participation in the trial will be informed of their disease status. Those with gingivitis will be provided with oral hygiene instructions. Those with periodontitis will be advised to seek treatment and will be provided with information about dental facilities that could provide care. Subjects who enroll in the trial will have inflammatory periodontal disease (gingivitis and/or periodontitis), and it is possible they will experience no improvement in their condition during the study. Subjects will be informed of their disease status at enrollment and will be told that they may need to seek periodontal treatment after their participation in the trial is completed. At the conclusion of their study participation, those with gingivitis will be provided with oral hygiene guidance, and those with periodontitis will be advised to seek treatment and will be provided with information about dental facilities that could provide care.

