3.2 Study Outcome Measures

3.2.1 Primary

The primary outcome measure of this study is safety, which will be assessed by the incidence of AEs, development or progression of periodontitis and changes in the oral flora.

Adverse events will be recorded throughout the study, and may include events reported by subjects or changes observed in oral cavity examinations or vital signs (assessed at baseline, Days 3, 7, 14, 21, and 28). Blood and urine will be collected for safety laboratory tests at Days 14 and 28 after product administration. Subjects will undergo close monitoring for mucosal inflammation and irritancy.

Subjects will be monitored for the development of or the progression of existing periodontitis, using standard clinical periodontal measurements. Development or progression of periodontitis will be determined by an increase of 2 mm or more in pocket depth or clinical attachment level (CAL) from the Day 0 baseline measurement ([Goodson et al, 1982](#)).

Each subject's oral flora will be analyzed in a pooled plaque sample collected from the mesiobuccal surfaces of the Ramfjord teeth at the Baseline Visit and at Days 14 and 28 of the experimental period. Using the deoxyribonucleic acid (DNA)-DNA hybridization (checkerboard) method ([Socransky, Smith et al. 1994](#), [Socransky, Haffajee et al. 2004](#)),

samples will be analyzed for the presence of the following species: *Fusobacterium nucleatum subspecies vincentii*, *Campylobacter concisus*, *Campylobacter rectus*, *Tannerella forsythensis*, *Prevotella intermedia*, *Prevotella nigrescens*, *Porphyromonas gingivalis*, *Capnocytophaga sputigena*, *Streptococcus oralis*, *Actinomyces naeslundii*, *Actinomyces israeli*, *Eubacterium brachy*, *Eikenella corrodens*, and spirochetes.

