7.3 Enrollment/Baseline

Study Visit 1 - Enrollment/Baseline Visit (Day 0)

- Obtain and document consent from subject on study consent form.
- Review and confirm medical and dental history, including alcohol and tobacco use history, for study inclusion.
- Record vital signs (temperature, pulse rate, respiratory rate, blood pressure).
- Record current concomitant medications and dental procedures and update medication history for study inclusion.
- Obtain urine pregnancy test on women of childbearing potential. Study staff will record the test kit lot, expiration date, and result. Test must be documented as negative before continuing to conduct baseline procedures that follow.
- Perform intraoral and extraoral examinations, to include hard and soft tissue assessments (face, lymph nodes, lips, buccal mucosa, floor of the mouth, tongue, hard and soft palate, gingiva, edentulous ridges, and teeth).
- Collect GCF for baseline measurements of IL-1 β .
- Assess and record baseline MGI.
- Assess and record baseline PI.
- Obtain supragingival plaque samples for baseline analyses of oral bacteria.
- Assess and record baseline PD and GM-CEJ distance (to calculate CAL).
- Assess and record baseline BOP.
- Reconfirm eligibility prior to subject randomization based on information collected during Screening Visit and study Visit 1.
- Obtain approximately 15 mL blood for baseline BLXA4 level and specialized pro-resolution mediator (SPM) (lipoxins and resolvins) profiling.
- Randomize subject to 1 of the study arms, using a block randomization schedule.
- Provide study drug with instructions for use and a timer to be used while rinsing. A study team member other than the examiner will supervise the subject's first use of the medication.
- Provide subject with the memory aid and instructions for its use.
- Provide subject with a study contact number to call for AEs or questions.

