 - 1 = film at the gingival margin
 - 2 = moderate (easily visible)
 - 3 = abundance of material

Periodontal measurements obtained on Days 14 and 28 will be compared with measurements obtained at Baseline to monitor subjects for development of or progression of periodontitis, defined for this study as an increase of 2 mm or more in pocket depth or CAL from the Day 0 baseline measurement.

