8.2 Progression of Periodontitis

Progression of periodontitis will be defined as an increase of 2 mm or more in pocket depth (PD) or clinical attachment level (CAL) from the Day 0 baseline measurement. The frequency (percent) of subjects with progression of periodontitis will be summarized by study arm, visit, and overall. Generalized linear mixed models regression based on a binomial distribution and logit link will compare the odds ratios of the overall incidence of the progression of periodontitis among the study arms at the Day 14 and Day 28 time points. The results of the generalized linear mixed model will be presented in a table and include p-values and odds ratios (with 95% CI) for the treatment arm comparisons at the two study visits. The p-values will not be adjusted for multiplicity.

The generalized linear mixed models analyses will automatically adjust for any missing values provided the missing values are missing at random; and thus, no additional imputation is necessary for missing values that are missing at random.

Missing observations are “not missing at random” if their missing-ness is possibly correlated with disease progression or efficacy. Missing PD or CAL observations due to missed visits or early study withdrawal will be deemed “not missing at random” if there were any treatment-emergent AE (TEAE) prior to or concurrent with a subject’s missed visit and the relationship between the TEAE and study drug was rated as “Possible”, “Probable”, or “Definite”.

If more than 5% of the PD or CAL measures are missing, or any missing PD or CAL measures are deemed “not missing are random”, then a sensitivity analysis will be performed by repeating the above generalized linear mixed model with all missing values imputed as having progression of periodontitis. The sensitivity analysis will also be triggered if for any other reason the principal investigator suspects that missing values may bias the analysis. The reasons a sensitivity analysis is triggered will be footnoted in the sensitivity analysis table.

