9.3.2.2 Sensitivity Analyses of Secondary Efficacy Outcomes

The exclusion criterion for periodontitis was removed in October 2015 for Protocol Version 4.0. This may change the study population by adding study participants with more advanced disease and possibly increase the variability in the effect sizes of the secondary efficacy outcomes. To explore the possible effects of changing the study population, sensitivity analyses will be performed for each of the secondary efficacy analyses. These sensitivity analyses will be performed similar to the secondary efficacy analyses but with the exclusion of subjects with periodontitis that would have been excluded in the original protocol. The results of the sensitivity analyses will then be compared to the secondary efficacy analyses to understand how removing the exclusion for periodontitis may affect the efficacy results.

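### SAP 8.2 compares the arms on periodontitis progression with no baseline periodontal covariate, so a realised imbalance in existing disease would carry into the odds ratio

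*Protocol*

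**What the plan says.** **The outcome.** Protocol 3.2.1: "The primary outcome measure of this study is safety, which will be assessed by the incidence of AEs, development or progression of periodontitis". Oral flora is the remaining component. An event is a rise of at least 2 mm in pocket depth (PD) or clinical attachment level (CAL) from the subject's own Day 0 value (Protocol 3.2.1 and 8.1.2; SAP 8.2). SAP 8.1 exempts progression, alone among the safety variables, from its rule against between-arm comparisons.

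**The model.** SAP 8.2: "Generalized linear mixed models regression based on a binomial distribution and logit link will compare the odds ratios of the overall incidence". Arms are contrasted at Days 14 and 28, with confidence intervals and p-values. No baseline term is named. By contrast, SAP 9.3.2.1 (efficacy) and SAP 9.3.3 (PD and CAL change) each name a baseline covariate in prose and in code.

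**The allocation.** Protocol 5.4.1: "Subjects will be assigned to treatment groups using a block randomization schedule". The Day 0 visit list in Protocol 7.3 repeats the method: "Randomize subject to 1 of the study arms, using a block randomization schedule". Neither place names a stratum.

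**The population.** Protocol 2.5.1 says that enrolled subjects have gingivitis, periodontitis or both. SAP 4 and 9.3.2.2 record that the periodontitis exclusion was dropped in October 2015. On the consequence, SAP 9.3.2.2 says: "This may change the study population by adding study participants with more advanced disease and possibly increase the variability in the effect sizes". That remark is about secondary efficacy. The SAP answers it with a sensitivity analysis excluding periodontitis subjects, for secondary efficacy only. The sensitivity analysis in SAP 8.2 concerns missing data only.

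**The data.** PD and the measurement that yields CAL are taken at Day 0 at 6 sites per tooth (Protocol 7.3 and 8.1.2).

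**The concern.** Measuring change from a subject's own baseline does not equalise the risk of crossing a 2 mm threshold. If people with periodontitis cross it more often, an arm that by chance holds more of them will show more progression whatever the rinse does. With arms of 50, 50 and 25, such imbalances are ordinary. An unadjusted logit model passes the imbalance into the odds ratio, where it could add to or mask a difference in a primary safety outcome. The trial already holds the measurement that would remove it. The issue is chance imbalance in the one allocation realised, not whether the drug effect differs by periodontitis status.

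**Working it through.** **The plan's own figures.** None is given for progression. The sizing figures reproduce and are not in dispute. For adverse events, 1 − 0.95^40 = 87.1%, as stated. For MGI, the SD of change is 0.3·√(2·0.7) = 0.355, which gives power of 71.2% and 53.9% by the normal approximation, against 70.9% and 53.8% stated.

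**Inputs.** Arms of 50, 50 and 25 are from the documents. The periodontitis share π (20%, 30%, 50%) and the progression risks with and without periodontitis (20% vs 10%, 20% vs 5%, 40% vs 10%) are assumptions.

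**Step 1: size of chance imbalance.** SD of the difference in share = √(π(1−π)(1/n₁+1/n₂)).
- 50 vs 50: 8.0, 9.2 and 10.0 points; times 1.96 gives 15.7, 18.0 and 19.6.
- 50 vs 25: 9.8, 11.2 and 12.2 points; times 1.96 gives 19.2, 22.0 and 24.0.
- If periodontitis subjects entered only after the exclusion was dropped, say 25 per arm with a 60% share: 1.96·√(2·25·0.24)/50 = 13.6 points.

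**Step 2: odds ratio with no drug effect.** Split the imbalance d evenly, so the shares are π ± d/2. Each arm's crude risk is share × (risk with) + (1 − share) × (risk without).

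Example (π = 30%, risks 40% vs 10%, 50 vs 50):
- 1 SD: shares 34.6% and 25.4%, crude risks 20.4% and 17.6%, odds ratio 1.20.
- 95% limit: shares 39.0% and 21.0%, crude risks 21.7% and 16.3%, odds ratio 1.42.

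**Step 3: compare with sampling error.** SE of the log odds ratio = √((2/50)/(p(1−p))), with p the pooled risk. The 95% CI factor is exp(1.96·SE).

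| Share | Risks with / without | OR at 1 SD | OR at 95% limit | 95% CI factor |
|---|---|---|---|---|
| 20% | 20% / 10% | 1.08 | 1.16 | 3.3 |
| 20% | 20% / 5% | 1.18 | 1.38 | 4.2 |
| 20% | 40% / 10% | 1.20 | 1.42 | 2.9 |
| 30% | 20% / 10% | 1.08 | 1.17 | 3.2 |
| 30% | 20% / 5% | 1.17 | 1.37 | 3.8 |
| 30% | 40% / 10% | 1.20 | 1.42 | 2.7 |
| 50% | 20% / 10% | 1.08 | 1.17 | 3.0 |
| 50% | 20% / 5% | 1.15 | 1.31 | 3.3 |
| 50% | 40% / 10% | 1.17 | 1.37 | 2.5 |

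An imbalance the other way gives the reciprocals. Against the no-rinse arm the 95%-limit odds ratio reaches about 1.5 (share 30%, risks 40% vs 10%: crude risks 22.3% and 15.7%), with a wider interval.

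**Step 4: does adjustment cut the standard error?** With balanced arms and no drug effect, the adjusted SE is √((2/50)/[π·p₁(1−p₁) + (1−π)·p₀(1−p₀)]), where p₁ and p₀ are the risks with and without periodontitis. It is slightly larger than the unadjusted SE: 0.615 to 0.620 (20% share, 20%/10%), 0.737 to 0.756 (20% share, 20%/5%) and 0.462 to 0.492 (50% share, 40%/10%).

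**Step 5: error rates.** These come from 40,000 simulated trials per scenario: 40 vs 40 completers, no drug effect, 5–10% progression without periodontitis, and a periodontitis odds ratio of 3–5. The comparison was between a simple unadjusted test and a Mantel-Haenszel test stratified on periodontitis, not the SAP's mixed model.
- Over all randomisations at a 30% share, the unadjusted two-sided error is 5.4–5.8%, close to nominal.
- Given 40% vs 20% periodontitis, the one-sided false harm signal (nominal 2.5%) is 5.7–7.6% unadjusted and 2.0–2.5% stratified. An imbalance of 20 points or more, in either direction, has a 3.5–9.3% chance at shares of 20–50%.

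**The case against.** The strongest reply is that the effect is small and its premise assumed. Much of this stands.

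- **Prognostic link.** Neither document says that existing periodontitis predicts a 2 mm rise within 28 days. SAP 9.3.2.2 speaks of variability in efficacy effects. No rule is stated for turning site readings into a subject-level event. With at least 20 teeth × 6 = 120 sites, probing error could matter more than disease status.
- **Size.** A 1-SD imbalance gives at most about 1.20. Even at the 95% limit, the shift in the log odds ratio is only about 0.24 to 0.7 of one standard error (for example, ln 1.16/0.615 and ln 1.42/0.510).
- **Weight.** Protocol 12.1 plans no formal test in the primary safety analysis, and 12.5.1 reports incidence by arm. The odds ratios come from the SAP, and the suspension criteria in Protocol 9.5 do not use them.
- **Silence.** SAP 8.2 is prose without code, and the randomisation schedule itself is not in view. Still, the SAP names a baseline covariate for its other models, so shorthand is the less likely explanation.

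A reader might infer more: that the unadjusted test is biased, that randomisation should have been stratified, or that a covariate would sharpen the estimate as in the linear efficacy models. None of these follows. Error over randomisations stays near nominal, the imbalance can be handled in the analysis, and Step 4 shows no gain in standard error. The reply does not remove the conditional point: once an imbalance has occurred, the planned odds ratio contains it.

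**Conclusion.** The point holds as a modest, low-cost improvement to SAP 8.2. The only formally compared safety variable, part of the primary outcome, is analysed in a mixed population with no baseline periodontal term named. If existing disease is prognostic, a realised imbalance moves a null test versus placebo odds ratio to about 1.08–1.20 at 1 SD and 1.16–1.42 at the 95% limit (50 vs 50), against a 95% CI factor of about 2.5–4.2. These ranges rest on assumed shares of 20–50% and the three assumed risk pairs. If existing disease does not predict a 2 mm increase, the shift disappears. The gain is a comparison that does not carry a visible imbalance, not a smaller standard error or the repair of an invalid test.

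**What to change.** Before the blind is broken (after database lock, per SAP 2.4), amend SAP 8.2:

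1. Add one baseline covariate to the progression model, preferably Day 0 full-mouth mean CAL or PD. Periodontitis status as classified for SAP 9.3.2.2 is an alternative, but it depends on the original protocol's exclusion criterion, so the SAP should write the definition out.
2. Tabulate progression by arm within baseline periodontitis status.
3. If events are sparse, use a stratified Mantel-Haenszel estimate or an exact or penalised one. State in advance that if the adjusted odds ratio cannot be estimated, only the stratified table is reported.

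The cost is one model term, one table split and a short definition. No new data are needed, and neither the randomisation nor the conduct of the trial changes. The downside is that with very few events the adjusted odds ratio may not be estimable. Choosing the covariate now also avoids the challenge that would meet an adjustment picked after an imbalance had been seen.
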